## **7.2 Analysis of the study**

Sensitivity, specificity, positive predictive value and negative predictive value will be calculated for

1. All specimens
2. Nasopharyngeal specimens only
3. Saliva specimens only

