## 1. PROTOCOL SYNOPSIS

Protocol title	Evaluation of novel molecular assays for the detection of influenza virus
Hypothesis	Our novel molecular assays for the detection of influenza A virus will be non-inferior to current molecular assays published by the World Health Organization and the US Centers for Disease Control and Prevention
Primary objective	To evaluate the sensitivity and specificity of different molecular assays
Clinical specimens	Nasopharyngeal and saliva specimens previously tested for influenza A virus
Study design	We will randomly retrieve archived nasopharyngeal and saliva specimens that were previously tested for influenza A virus using commercially available assays in our laboratory, tested for influenza A virus at the Public Health Laboratory Service Branch in Hong Kong. These specimens will be tested for influenza A virus by 4 different RT-PCR assays as listed below: 

1. Our new RT-PCR assay targeting PB2 gene

2. Our new RT-PCR assay targeting NS gene

3. M gene RT-PCR published by the World Health Organization

4. M gene RT-PCR published by the US CDC.

Primary outcome	Results of different RT-PCR assays
Secondary outcome	Cycle threshold (Ct) value of different RT-PCR assays
Data analysis	Sensitivity, specificity, positive predictive value and negative predictive value will be determined

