### **3. STUDY OBJECTIVES**

1. To evaluate the sensitivity and specificity of different molecular assays

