### **4. STUDY DESIGN**

#### **4.1. Overall study design**

We will randomly retrieve archived nasopharyngeal and saliva specimens that were previously tested for influenza A virus using commercially available assays in our laboratory, tested for influenza A virus at the Public Health Laboratory Service Branch in Hong Kong. These specimens will be tested for influenza A virus by 4 different RT-PCR assays as listed below:

1. Our new RT-PCR assay targeting PB2 gene
2. Our new RT-PCR assay targeting NS gene
3. M gene RT-PCR published by the World Health Organization
4. M gene RT-PCR published by the US CDC.

Sensitivity and specificity will be determined as we described previously [9].

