## 7. STATISTICAL METHODS

### **7.1 Sample size**

We will perform all 4 RT-PCR assays on a total of 320 specimens, including

- 80 nasopharyngeal specimens which tested positive for influenza A by commercially-available molecular assays or by testing performed at the Public Health Laboratory Services Branch in Hong Kong
- 80 nasopharyngeal specimens which tested negative for influenza A by commercially-available molecular assays or by testing performed at the Public Health Laboratory Services Branch in Hong Kong

- 80 saliva specimens which tested positive for influenza A by commercially-available molecular assays
- 80 saliva specimens which tested negative for influenza A by commercially-available molecular assays

The sample size is based on feasibility of the study

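### PPV and NPV are to be calculated in specimen sets made half positive by quota, so they reflect the sampling ratio and not predictive values in tested patients

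*Protocol*

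**What the plan says.** Protocol section 7.1 sets the sample by quota: "We will perform all 4 RT-PCR assays on a total of 320 specimens, including" four groups of 80. The saliva groups are "80 saliva specimens which tested positive for influenza A by commercially-available molecular assays" and "80 saliva specimens which tested negative for influenza A by commercially-available molecular assays". The two nasopharyngeal groups are split in the same way, except that testing at the public health laboratory also counts. The only reason given for the sample size is feasibility.

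Section 7.2 says: "Sensitivity, specificity, positive predictive value and negative predictive value will be calculated for" three sets, namely the pooled specimens, the nasopharyngeal specimens and the saliva specimens. The synopsis repeats the four measures: "Sensitivity, specificity, positive predictive value and negative predictive value will be determined".

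The single objective in section 3 is narrower: "To evaluate the sensitivity and specificity of different molecular assays". Section 4.1 refers to an earlier publication for the method, but only for sensitivity and specificity. The protocol states no prevalence of influenza A among tested patients, no reweighting of PPV or NPV, and no limit on the population to which they apply.

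**The concern.** Sensitivity is conditional on being positive by the reference, and specificity on being negative. Choosing how many of each to sample therefore leaves both intact. PPV and NPV condition the other way, on the new assay's result, and so depend on the proportion of positives in the set. Here that proportion comes from a quota and not from the patients who are tested. Random retrieval, as section 4.1 plans, does not help, because it operates within fixed quotas.

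PPV and NPV from these counts would change if the quota changed, although the assays had not. They are also the two measures a clinician is most likely to read as the meaning of a result for a patient. If prevalence in use is below 50%, PPV is overstated whenever specificity is below 100%, and NPV is understated whenever sensitivity is below 100%. Above 50% both directions reverse.

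**Working it through.** **Inputs from the protocol (section 7.1).** Four groups of 80: 4 × 80 = 320, which matches the stated total. With the earlier result as reference, the positive share is 160/320 = 50% pooled and 80/160 = 50% in each specimen type.

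**Assumed inputs.** The protocol gives no sensitivity (Se), specificity (Sp) or prevalence (p). I take Se = 95%, Sp from 95% to 100%, and p from 5% to 60%.

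**Formulas.**
- PPV = Se·p / [Se·p + (1 − Sp)(1 − p)]
- NPV = Sp(1 − p) / [Sp(1 − p) + (1 − Se)p]

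**Dependence on the quota.** Take Se = Sp = 95% in one specimen type.
- At 80:80 the expected counts are 76 true and 4 false positives, 76 true and 4 false negatives. PPV = 76/80 = 95.0% and NPV = 76/80 = 95.0%.
- At 40:120, with the same assay, they are 38 true and 6 false positives, 114 true and 2 false negatives. PPV = 38/44 = 86.4% and NPV = 114/116 = 98.3%.

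**PPV by prevalence (Se = 95%).**

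| Sp | 50% (design) | 20% | 10% | 5% |
|---|---|---|---|---|
| 95% | 95.0% | 82.6% | 67.9% | 50.0% |
| 98% | 97.9% | 92.2% | 84.1% | 71.4% |
| 99% | 99.0% | 96.0% | 91.3% | 83.3% |
| 100% | 100% | 100% | 100% | 100% |

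Example: Sp = 95%, p = 10% gives 0.095 / (0.095 + 0.05 × 0.90) = 0.095/0.140 = 67.9%.

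**NPV.** Over the same specificities it is 95.0% to 95.2% at the design's 50%, and 99.4% at p = 10%. It shifts even when specificity is 100%.

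**Reversal above 50%.** At p = 60% and Se = Sp = 95%, PPV is 96.6% and NPV 92.7%.

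**Intervals, pooled set.** Suppose 152/160 true positives and 2/160 false positives (Se = 95%, Sp = 98.75%).
- Raw PPV = 152/154 = 98.7%, Clopper-Pearson 95% CI 95.4% to 99.8%.
- For the Bayes value, the variance of logit(PPV) is (1 − Se)/(160·Se) + Sp/[160(1 − Sp)] = 0.0003 + 0.4938 = 0.494, so SE = 0.703.
- At p = 10%: PPV 89.4% (68.0% to 97.1%). At p = 5%: 80.0% (50.2% to 94.1%).

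**Intervals with no false positives.** The point estimate of PPV is then 100% at every prevalence, so only lower limits should be compared. The Bayes column inserts the Clopper-Pearson lower limit for specificity, with Se = 95%.

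| Counts | Raw PPV lower limit | Sp lower limit | PPV at that Sp, p = 10% | p = 5% |
|---|---|---|---|---|
| 152/160, 0/160 | 97.6% | 97.7% | 82.2% | 68.7% |
| 76/80, 0/80 | 95.3% | 95.5% | 70.1% | 52.6% |

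**Ranking.** odds(PPV) = [Se/(1 − Sp)] × p/(1 − p), and odds(NPV) = [Sp/(1 − Se)] × (1 − p)/p. Prevalence multiplies every assay's odds by the same factor, so the order of the four assays at a common prevalence does not change.

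**The case against.** The strongest reply is that the reach is small. PPV and NPV appear only in the lists of measures and are tied to no objective, hypothesis or decision rule. The protocol states the 1:1 split openly, describes the sets simply as specimens, and never claims that the values apply to patients. On that view this is a labelling matter for the report. Most of this stands, and it limits the weight of the point. But the protocol commits to calculating two measures in sets that cannot support them without an outside prevalence, and includes no label.

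A second reply is that an SAP, not shown here, may supply a prevalence and an adjustment. It could. Still, the protocol itself names both the measures and the sets, and direct calculation is the natural reading. The cited earlier method is invoked for sensitivity and specificity only.

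Third, the reference standard is not named, so the exact 50% is conditional. That is correct. A composite standard could move the share somewhat, but the quota would still largely determine it.

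Fourth, the size depends on the assumptions. The fall from 95.0% to 50.0% needs both 95% specificity and 5% prevalence. At 99% specificity and 20% prevalence the change is only from 99.0% to 96.0%, and at 100% specificity PPV does not move. This also stands. However, even no false positives among 160 negatives shows only that specificity is at least 97.7%, and NPV moves whenever sensitivity is below 100%.

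**Conclusion.** The concern holds and should be fixed. As planned, absolute PPV and NPV would apply only where half of those tested are infected, and nothing in the protocol supports that figure. With sensitivity at 95%, the overstatement of PPV at 10% prevalence is 27.1 percentage points at 95% specificity (95.0 − 67.9), 7.7 at 99% (99.0 − 91.3) and nil at 100%. NPV is understated by about 4 points. The raw interval is also too narrow for use at low prevalence.

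The conclusion assumes that the earlier result is the reference and that the values come directly from the counts. The sizes rest on assumed accuracy and prevalence. Confidence in the principle is high. The effect is confined to PPV and NPV: the sole objective is untouched, and so is the ordering of the assays at a common prevalence.

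**What to change.** In section 7.2 and in the data analysis row of the synopsis, do one of the following:

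- delete PPV and NPV, leaving sensitivity and specificity, which match the objective; or
- derive PPV and NPV by Bayes' formula from the estimated sensitivity and specificity at stated prevalences (for example 5%, 10% and 20%, or the laboratory's own positivity rate), with intervals that carry the uncertainty in both.

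If raw values are still shown, state beside them that they apply only to the 1:1 sample.

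The cost is a change of wording in two places and a little extra calculation. No specimens or tests are added. The reported PPV may be lower and its interval wider.
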